14.2.5.2 Analysis of Tolerability

Tolerability will be assessed using the scale in Section 12.2. For each of the assessments, the proportion of subjects experiencing none, mild, moderate, and severe will be summarized by visit.

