
Test product, dose and mode of administration:

Obagi 360 System consisting of: Obagi 0.5% retinol, Hydrafactor SPF30, and Exfoliating cleanser. The system will be used once daily for 3 months.

Reference therapy, dose and mode of administration:

None

Duration of treatment, enrollment and follow-up:

Duration of treatment period: 12 weeks

Criteria for evaluation:

- 1. Improvement in manifestations of photodamage assessed by the investigator using the Investigator's Skin Grading Assessment.
- 2. Assessment of improvement by the subject using the Subject's Self-Assessment.

Safety:

Safety variables include treatment-emergent adverse events (AEs), serious AEs (SAEs), treatment related AEs, and AEs leading to study discontinuation.

The investigator will assess the tolerability of the product at each visit.

Sample size:

Forty subjects will be enrolled. Forty (40) subjects are adequate to obtain information on the anti-aging effects of the Obagi 360 system.

Statistical methods:

The effect of the Obagi 360 system on photodamage will be evaluated using the Investigator's Skin Grading System. The changes from baseline in the scores will be summarized and tested for significance using the paired T-test for each time point. In addition, a summary of the distribution or scores (improvement or worsening) will be summarized and categorized as the number and proportion of subjects "Improved", "Equal to" or "Worse" than baseline.

For the Subject's Self-Assessment, the response to each question will be summarized by the proportion of subjects in each category. No statistical testing will be performed on the Subject's Self-Assessment.

Safety will be summarized by the incidence of adverse events over the study by body system and preferred term. The tolerability will be summarized by the proportion of subjects with none, mild, moderate, and severe for each assessment by visit.

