7.3 SCHEDULE OF STUDY PROCEDURES

A table outlining the schedule of procedures for this study is presented in Table 1.

Table 1 Procedures Flow Chart

PROCEDURES	BASELINE (DAY 0)	DAY 14 (± 2 Days) and DAY, 28, 56, and 84 (± 5 Days)
	Visit 1	Visits 2 through 5
Obtain Informed Consent, HIPAA Authorization	X	
Obtain Photographic Release Form	X	
Review Inclusion/Exclusion Criteria	X	
Review Medical History	X	
Obtain Subject Demographics	X	
Conduct Investigator's Skin Grading Assessment	X	X
Urine Pregnancy Test ¹	X	X
Obtain Photographs	X	X
Conduct Subject's Self-Assessment ²		X
Assign Subject Number	X	
Review Obagi 360 Application ³	X	X
Dispense/Collect Obagi 360 System	X	X
Assess Tolerability		X
Review Concomitant Medications	X	X
Review Adverse Events		X
Review Compliance with Study Procedures		X

UPT obtained on subjects of child bearing potential only.

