8.5 STUDY SUBJECT WITHDRAWAL OR EARLY TERMINATION

8.5.1 WITHDRAWAL/EARLY TERMINATION

An early termination occurs when an enrolled subject ceases participation in the study, prior to completing the protocol. Subjects must be permitted to withdraw from the study at any time for any reason. Subjects may be withdrawn at any time at the discretion of the investigator or sponsor for safety, compliance, or other reasons. In general, subjects should not be withdrawn by investigators prior to completion of the study unless there is documentation of any of the following:

- The investigator believes that the subject has experienced significant or disabling treatment-related adverse events (AEs) that can be diminished or avoided by subject withdrawal. Discussion with Obagi prior to withdrawal is preferred.
- Subject withdrawal is in the best interest of the health of the subject. A withdrawal for medical reasons should document the specific condition for removing the subject.
 Discussion with Obagi prior to withdrawal is preferred.
- Lost to follow-up.
- Death.

The final safety evaluation required by the protocol will be performed at the time of the early termination, if possible. All subject withdrawals will be fully documented.

Subjects who discontinue prematurely from the study will not be replaced until approved by the sponsor.

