12.2 TOLERABILITY EVALUATIONS

The investigator will assess the tolerability of the Obagi 360 system at each visit. Tolerability will be graded on a 4-point scale (0 - none to 3 - severe) for each of the following:

- Dryness/Scaling
- Erythema
- Burning/Stinging
- Itching

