14.2.5 ANALYSIS OF SAFETY

14.2.5.1 Analysis of Adverse Events

Safety analysis will include assessment (number and %) of all treatment-emergent AEs, any serious AEs, treatment-related AEs, and AEs leading to study discontinuation for each treatment group.

All AEs will be coded by the Medical Dictionary for Regulatory Activities (MedDRA).

Treatment-emergent adverse events (TEAEs) are defined as those AEs that either have an onset time on or after the start of study drug until the end of study.

Treatment-emergent AEs will be summarized for each treatment group by the overall incidence of at least one event, incidence by system organ class, and incidence by system organ class and CONFIDENTIAL AND PROPRIETARY INFORMATION OF OMP, INC.

preferred term. Each subject will be counted only once for each of the rates, regardless of the number of occurrences (events) the subject experiences. Treatment-emergent AEs will be summarized by severity and by relationship to study product.

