14.3 SAMPLE SIZE

Forty subjects will be enrolled. Forty subjects are adequate to obtain information on the antiaging effects of the Obagi 360 system.

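### By-visit tolerability proportions do not show how many subjects ever had a local reaction; add a worst-grade-per-subject summary (minor)

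*Protocol*

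**What the plan says.** Section 12.2 has the investigator grade dryness/scaling, erythema, burning/stinging and itching from 0 (none) to 3 (severe). Table 1 in Section 7.3 marks this assessment only in the column for "Visits 2 through 5", that is Days 14, 28, 56 and 84. It has no mark at baseline and there is no early-termination column.

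The planned summary is given twice, consistently. Section 14.2.5.2: "the proportion of subjects experiencing none, mild, moderate, and severe will be summarized by visit". Synopsis, statistical methods: "The tolerability will be summarized by the proportion of subjects with none, mild, moderate, and severe for each assessment by visit". Neither place mentions a worst grade per subject or a count of subjects ever affected.

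Three other provisions bear on the point:

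- **Early leavers.** Section 8.5.1 states: "The final safety evaluation required by the protocol will be performed at the time of the early termination, if possible". It does not say whether the four signs are graded then.
- **Adverse events.** Section 14.2.5.1 does count by subject over the study: "Treatment-emergent AEs will be summarized for each treatment group by the overall incidence of at least one event", and "Each subject will be counted only once for each of the rates, regardless of the number of occurrences (events) the subject experiences".
- **Population.** Section 14.1 assigns the safety population (everyone enrolled who applied any product) to all safety analyses. The denominator for each visit row is not stated.

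**The concern.** This is a single-arm study of a retinol-containing regimen, and the four graded signs are its systematic, solicited record of local reactions. A reader will want to know how many of the 40 subjects had a moderate or severe reaction at some point. Four separate cross-sections do not answer that, because they do not show whether the same or different subjects are affected from visit to visit.

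Loss of subjects adds to the problem. Section 8.5.1 lists significant or disabling treatment-related adverse events among the grounds for withdrawal, so subjects who react may leave. Later rows would then describe those who remained, and a falling proportion could be read as irritation fading with use.

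**Working it through.** The protocol states no irritation rate and no precision target for tolerability, so there is no figure of its own to reproduce. What can be checked is how much the planned table determines.

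**Inputs.** N = 40 (Section 14.3: "Forty subjects will be enrolled"). Four tolerability visits (Table 1). The proportion p affected at each visit is assumed, and no data are missing.

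**Formulas** for the proportion ever affected over four visits:

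- same subjects at every visit (lower bound): p
- visits independent: 1 − (1 − p)^4
- different subjects at every visit (upper bound): min(1, 4p)

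| Assumed p per visit | Subjects per visit | Same subjects | Independent | All different |
|---|---|---|---|---|
| 5% | 2 | 5% | 1 − 0.95^4 = 18.5% | 20% |
| 10% | 4 | 10% | 1 − 0.90^4 = 34.4% | 40% |
| 20% | 8 | 20% | 1 − 0.80^4 = 59.0% | 80% |

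At 10% per visit the three situations give identical by-visit tables, yet the number ever affected runs from 4 to 16 of 40.

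A falling pattern behaves the same way. With assumed proportions of 30%, 20%, 10% and 5%:

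- lower bound: 30%, the largest row
- independent: 1 − 0.70 × 0.80 × 0.90 × 0.95 = 52.1%
- upper bound: 30 + 20 + 10 + 5 = 65%

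With complete data the largest single row is therefore a lower bound. It equals the cumulative figure only if everyone ever affected is affected at that visit.

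**Early leavers, two assumed cases:**

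1. Four of 40 subjects are severe at Day 14 and leave; nobody else is severe. The rows read 4/40, then 0/36 three times. The cumulative figure, 4/40 = 10%, is visible in the Day 14 row. Only the apparent improvement is an artefact of who remained.
2. Four of 40 subjects are grade 0 at Day 14 and leave because of a reaction before Day 28; nobody else reacts. The scheduled rows read 0/40, then 0/36, while 4/40 = 10% reacted. The scale can show these four only if it is graded at early termination and that grade is tabulated.

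**Does the adverse event table fill the gap?** Only in part:

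- Section 12.1 defines adverse events broadly enough to include a sign or symptom that appears or worsens. However, nothing in the protocol says that a tolerability grade above 0 must also be recorded as an adverse event.
- Section 12.1 has the investigator ask about adverse events without leading the subject, whereas Section 12.2 has the investigator grade four named signs. Visible scaling or erythema could be graded without being reported as an event.
- Section 12.1.1 grades adverse event severity largely by tolerance and effect on usual activity. That is a separate scale from the one in Section 12.2, so adverse event severity cannot stand in for the worst tolerability grade.

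**The case against.** The strongest reply is that the protocol already has a subject-level safety summary. Section 14.2.5.1 counts each subject once, by severity and relationship, and reports events leading to discontinuation; Section 14.2.1 adds reasons for discontinuation. Irritation recorded as an adverse event is therefore added up across visits, including for early leavers. This stands, and it narrows the gap to reactions that are graded but not recorded as events.

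A second reply is that by-visit grading is a legitimate display of time course, and that worst-grade tables and the handling of off-schedule assessments often sit in the SAP, which was not available here. That also carries weight. Still, the protocol specifies its tolerability summary in two places, and as specified it cannot give the subject-level result. If the SAP already adds a worst-grade table, the point is met.

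A reader might infer more than the text supports:

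- **That the planned table understates how many subjects the product irritated.** Each row is correct for its visit and makes no cumulative claim. Any understatement comes from reading one row, or a falling trend, as the study total. Its size, possibly zero, cannot be derived from the protocol.
- **That an early-termination grade is shut out of the table.** The protocol does not say whether the signs are graded at early termination or how such a grade would be tabulated. Silence is not exclusion.
- **That a worst-grade count would measure product-caused irritation.** With no baseline grade, dryness or erythema present before treatment would be counted too.

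**Conclusion.** The point holds in limited form and is minor. The by-visit proportions in Section 14.2.5.2 and the synopsis are valid descriptions of each visit, but they do not determine how many subjects ever had a mild, moderate or severe reaction, and later rows can look better if subjects who reacted have left. The adverse event incidence in Section 14.2.5.1 closes this only for reactions also recorded as adverse events.

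The range of 4 to 16 of 40 illustrates the indeterminacy under an assumed 10% per visit and complete data; it is not a prediction. The qualitative conclusion does not depend on that rate: whenever reactions of a given grade occur at more than one visit, the rows alone generally bound the cumulative number and do not fix it.

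**What to change.** In Section 14.2.5.2, and correspondingly in the synopsis:

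1. Keep the by-visit table and show the number assessed at each visit.
2. Beside it, add for each of the four signs the number and percentage of the safety population by worst post-baseline grade over the whole study, including any early-termination or unscheduled grade.
3. Describe the added table as reactions during treatment, not as irritation caused by the product, because tolerability is not graded at baseline.
4. State when a tolerability grade is also recorded as an adverse event, so that the two summaries can be read together.

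The added table uses data already collected; item 4 is one sentence. The downsides are that the headline figure may be less favourable than any single visit row and may include dryness or erythema that was present before treatment.

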14.3 SAMPLE SIZE

Forty subjects will be enrolled. Forty subjects are adequate to obtain information on the antiaging effects of the Obagi 360 system.

14.4 INTERIM REPORT

Interim analyses are not planned for this study.

14.5 DATA HANDLING

Standards for data handling will be established in the data management plan. Study data will be reviewed, according to these data management guidelines. Case report forms will be monitored and audited by Obagi. Data management will provide queries for discrepancies requiring study center resolution. Upon receipt of resolved queries, appropriate updates, based on the response, will be made to the database. New or changed information in each query must be verifiable in the source documentation.

15 MANAGEMENT/COMPLIANCE/QUALITY ASSURANCE

15.1 STUDY TERMINATION

The protocol may be terminated by Obagi immediately upon notice to the investigator, if any of the following conditions occur:

- If the emergence of any adverse reaction or side effect with the study product in the study or elsewhere is of such magnitude or incidence in the opinion of Obagi to support termination.
- Obagi may also terminate the study for any internal business reasons at Obagi's sole discretion.
- If Obagi fails to secure compliance with requirements of the protocol and GCP at a specific site the study must be terminated at that site.

In the event of a termination, Obagi will provide information on the handling of currently enrolled subjects who have not completed the protocol.

15.2 MONITORING

Monitoring visits provide Obagi with the opportunity to evaluate the progress of the study, verify the accuracy and completeness of CRFs, assure that all protocol requirements, investigator's obligations are being fulfilled, and resolve any inconsistencies in the study records. Monitoring is required by federal regulations. The investigator will allow Obagi representatives to periodically review, at mutually convenient times during the study and after the study has been completed, all CRFs and corresponding portions of office, hospital, and laboratory records (source documents) of each study participant. CRFs must be up-to-date and available for each monitoring visit. The investigator or appropriate personnel must be available during the monitoring visits.

15.3 OBAGI AUDITS/QUALITY ASSURANCE

Obagi may require a site audit for cause The investigator or appropriate personnel must be available during audits.

Quality assurance includes verification of data entered into the study database via the query process. In the event of inconsistent or missing data, the discrepancies will be clarified by the issuing of query forms to the site for resolution. The study database cannot be closed until all queries are addressed. Prompt response to queries is required.

15.4 CASE REPORT FORMS (CRF)/SOURCE DOCUMENTS

Case report forms (CRFs) will be used for recording all data from source documents for each subject. Source documents are the point of first entry for all data collected, and may include written charts, laboratory results, diaries and questionnaires. Relevant data will be entered into the case report form system. Data should be entered within one week of each subject's visit, if possible. Whenever possible, an original recording of an observation should be retained as source document. Specific training will be provided to center personnel prior to study start.

The investigator will ensure that the CRFs are properly completed for all subjects who have signed an informed consent form. CRFs will be monitored against source documents. If data in the CRF are not duplicated in a source document, a source document should be created and maintained by the site to capture that information. Source documentation for subjects include but are not limited to the physician's patient records or hospital computer database, diaries, photographs, x-rays and electrocardiograms. All source documents will be maintained at the study site.

The principal investigator or delegate may enter corrections in the CRFs. Each change will be initialed and dated in black ink by the person performing the change. The final CRF will be approved by the principal investigator by signature.

15.5 STUDY RECORDS/SOURCE DOCUMENTS MAINTENANCE

All records pertaining to the conduct of the clinical study, including signed CRFs, informed consent forms, drug accountability records, source documents, and other study documentation must be retained until notified by Obagi

In any case, the investigator must not destroy any records associated with the study without contacting Obagi and receiving approval. The investigator must notify Obagi in the event of accidental loss or destruction of any study records. If the investigator leaves the institution where the study was conducted, Obagi must be contacted to arrange alternative record storage options. Study documentation includes, but is not limited to, all CRFs, data correction forms, source documents, monitoring logs, Obagi-investigator correspondence, protocols and amendments, clinical supplies receipt, dispensing and final disposition records, IRB correspondence and approvals, signed consent forms, and Statement of Investigator forms.

15.6 PROTOCOL COMPLIANCE

The investigator must comply with all terms of the protocol. All protocol deviations must be documented. The subject is also expected to comply with the protocol as set forth in the informed consent and implicit in subject participation. During the recruitment phase, it is imperative that the subjects understand that they are expected to return for the designated follow-up treatment and evaluations, and the importance of doing so. If the subject is not willing to participate in the follow-up, he/she must be excluded from participation.

15.7 PROTOCOL AMENDMENTS

Any amendment to the protocol, with the exception of those which remove an emergency or immediate health risk to the subject, must be approved in writing by the IRB and Obagi before implementation. The provisions for emergency amendment require, if feasible, prior contact with Obagi, and the IRB. If contact is not feasible before the change, Obagi and the IRB must be contacted as time permits. All changes to the final study protocol must be documented in a written protocol amendment either before implementation or, in the event of an immediate health hazard, within 5 working days.

15.8 DEVIATION FROM THE PROTOCOL

The investigator should not deviate from the protocol. In medical emergencies, the investigator will use medical judgment and remove the participant from immediate hazard as discussed above.

Deviations from the protocol may nevertheless occur (e.g., subject failure to attend scheduled visit during a visit window, accidental omission of notations from the CRF, misunderstanding with regard to visit procedures). Any deviation from the protocol must be fully recorded in the

CONFIDENTIAL AND PROPRIETARY INFORMATION OF OMP, INC.

source documents to permit analysis of the effect of the deviation on the data collected, subject safety, or data analysis.

Deviations from the protocol must be reported to the IRB according to their policies.

15.9 CONFIDENTIALITY/STUDY SUBJECT IDENTIFICATION

All information not previously published concerning the test product and Obagi's research, including patent applications, manufacturing processes, basic scientific data, this protocol, or other information provided by Obagi, is considered confidential and should remain the sole property of Obagi, pursuant to the written contractual agreement between these parties which governs the handling of Proprietary and Confidential Commercial Information. The investigator agrees to use the information only in connection with this study and will not use it for other purposes without written permission from Obagi. The terms of the Investigator Agreement govern the definition and handling of confidential information.

It is understood by the investigator that data from the study may be used by Obagi in connection with the development of the study product. Data and information may therefore be disclosed as required to other investigators or be placed in the product label or other information disseminated by Obagi. By signing this protocol, the investigator affirms that study subject data, and especially study subject identifier information, will be maintained in confidence as set forth in the protocol and any written contractual agreement. Confidential information will be divulged to the IRB, IEC, or similar expert committee; affiliated institutions; and employees only under an appropriate understanding of confidentiality with such board or committee, affiliated institution and employees. By signing the protocol, the investigator agrees that, within local regulatory restrictions and ethical considerations, Obagi or representatives of Obagi, or applicable regulatory agency may review study documents, including study subject identifying and other confidential information, in order to verify CRF data and in accordance with federal regulations. Obagi shall, to the extent feasible, protect study subject identifier information.

15.10 COMPLIANCE WITH THE LAW

By signing this protocol, the investigator agrees to conduct the study in an efficient and diligent manner and in conformance with the protocol, generally accepted standards of good clinical practice, conditions of protocol approval imposed by the IRB, and all applicable federal, state and local laws, rules and regulations. The investigator shall prepare and maintain complete and accurate documents relating to the investigation in compliance with the protocol, GCP standards and applicable federal, state and local laws, rules and regulations including all correspondence with another investigator, an IRB, Obagi or monitor and each subject's case history and exposure to the investigational product as required on the CRFs and maintain all supporting data in subject records. For each study subject participating in the study, the investigator will promptly submit all original CRFs to Obagi. Furthermore, the investigator also agrees to submit other necessary documents as required by this protocol following completion or termination of the clinical

CONFIDENTIAL AND PROPRIETARY INFORMATION OF OMP, INC.

evaluation or as otherwise required pursuant to any agreement with Obagi or Representative of Obagi. Study documents will be promptly and fully disclosed to Obagi by the investigator upon request for inspection, copying, review and audit at reasonable times by representatives of Obagi. The investigator agrees to promptly take any reasonable steps, requested by Obagi or representative of Obagi, as a result of an audit, to cure deficiencies in the document or CRFs. The investigational product will be used only on subjects properly enrolled in the study. Upon completion or termination of the study or the investigator's participation in the study, the investigator will account for and/or return to Obagi any remaining supply of the investigational product as Obagi directs. The investigator will maintain records of receipts, type and quantity, dates of receipt, batch numbers, and the names of all persons who may have received used or disposed of each investigational product and whether and how any such products were returned, repaired, or destroyed. The study product will be stored in a secure location. The investigator shall record any deviations from protocol management of a subject. The investigator will maintain a signed copy of the protocol.

